Choice of method: This study has an exploratory design and aims to investigate decision-making processes regarding choices where the informants can't be exposed to an experimental decision due to both the nature of the choice and seriousness of the consequences. Despite its well-acknowledged weaknesses, hypothetic scenario-based survey research emerged as a suitable approach based on a mapping review of the medical literature and on transferred knowledge derived from decision-

making research in other fields where decisional stakes are high as for example in criminology, economy, and politics [9-12].

We plan to develop and to validate a survey instrument and to conduct a self-administered survey of Norwegian residents aged 80 and older and a close family member who likely would act as a proxy in an event of acute illness.

Target population and sampling frame: Due to ethical concerns regarding exposure of very elderly patients to hypothetical treatment choices which they in real life would not be offered, we attempt to exclude patients who are not regarded potential ICU candidates in Norway owing to low physical and/or cognitive function. Furthermore, we have limited knowledge on whether very elderly people in Norway might experience a questionnaire addressing critical illness and risk of dying as a burden. We prefer therefore a sampling method where the informants have a short face-to-face encounter with one of the investigators followed by the offer to re-contact by phone or e-mail in case of emotional distress related to completing the questionnaire. For these two reasons, we abandoned the idea of a mailed survey to a random generated population-based sample and decided to study a purposive sample of potential ICU candidates aged 80 years or more.

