Survey construction: Table 1 summarizes the structure of the questionnaires. They start with a short summary of background information regarding intensive care in general, and expected risks and benefits for very elderly patients in particular. Then the participant is asked to make a treatment choice regarding four clinical vignettes; the very elderly person is asked only about his or her own preferences, while the proxy is asked to both indicate the likely wish of the very elderly person, and his or her own preference. Three response options are provided: wishing admission to intensive care, not wishing admission to intensive care, and wishing to not engage in the decision.

	Very elderly person (potential patient)		Potential proxy	
Cover / instructions / contact information (p.1) Background information (p.2)				
	Paragraph no.	Questions	Paragraph no.	Questions
Vignettes/scenarios 1–4	1-4	4 x 3	1-4	4 x 6
Family involvement in medical decision-making	5	5	5	3
Experiences with intensive care and advanced care planning	6	5	6	6
Demographics	7	7	9	7
Health / frailty	8	5	7	5
EuroQuol		6	8	6
Comments	9	1	10	1
Re-contact permission	10	1		
Pages / questions (total)	15 / 42		18 / 53	

Table 1: questionnaire structure

The vignettes are randomly chosen among 20 hypothetical patient histories of acute life-threatening illness causing a higher degree of acute organ failure (equaling > 2 SOFA points) [13].

All vignettes are built up in a similar way, containing three paragraphs, following the same template:

1. 2–3 sentences regarding the current diagnosis and acute organ failure. The type and frequency of diagnoses is representative for ICU admission diagnosis in elderly patients in Norway and Europe (table 2). For each questionnaire, there will be four vignettes – two framed as a history of a male patient, and two framed as a female patient. The vignettes will be presented in a random order.
2. 3–4 sentences describing dichotomous therapeutic options as either intensive care with sedation requirements and some kind of invasive organ support or ward care with conservative treatment and the possibility for symptom alleviation.

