3. 3 sentences on the consequences of the choice. The survival outcome estimates are based on short- and long-term outcome data from the VIP2- study data-set (table 2). The estimated quality of life regarding physical and cognitive function of ICU survivors aged ≥ 80 years is based on published data from Norway, Finland, the Netherlands and Canada [14-17], and a systematic review on cognitive impairment after intensive care [18]. Outcomes are identical for all vignettes, but in 50% of the questionnaires, the expected outcome is framed as mortality and in 50% as survival. The same framing is used for all four vignettes in each questionnaire.

ICU admission diagnosis	VIP-2 (May 2018-May 2019)					NIR (May 2018-May 2019)		
	N (%)	Survival (%)			N (%)	Survival (%)		
		ICU	30 d	6 m		ICU	30 d	1 y
Overall	3921 (100)	73	75	40	3069 (100)	86	67	47
ARF	941 (24)	75	76	34	951 (31)	84		
Sepsis	392 (14)	68	70	33	338 (11)	86		
Shock	540 (14)	72	71	34	737 (24)	88		
Acute surgery	541 (14)	80	82	45	614 (23)	86		
Trauma	233 (6)	69	70	30	215 (7)	85		
Neuro	190 (5)	68	68	30	153 (5)	87		

Table 2: Main admission diagnosis and survival of very elderly (≥ 80 år) ICU patients in Europe (VIP-2 data set, personal communication, [name], April 2021) and in Norway (NIR (Norwegian Intensive Care Registry), personal communication, [name], April 2021)

Furthermore, the survey covers items that may influence treatment preferences and proxy accuracy including: demographics, education, religion, previous experience with and / or communication about serious illness, comorbidity (Charlson Comorbidity Index, [19]), frailty (Clinical Frailty Scale, version 2, [20]), quality of life (EuroQol-5D-5L, registration ID: 30864, [21]) and projection (i.e. the proxy's own treatment preferences, [8]). Items were generated by a mapping review of the existing literature on elderly patients' treatment and end-of-life preferences and on proxy accuracy in general. Additional items were identified by discussions within the research group.

The questionnaires ask for the following free-text comments:

- Elaborating the treatment choice made after each scenario
- Expectations regarding family members contribution into the decisional process
- General comments

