The above calculations are based on simple logistic regression, i.e., assuming that only *one* preference (from one patient vignette) is expressed for each participant. In practice, there will be four (correlated) preferences for each participant, and we will use statistical methods that take this into account (mixed-effects logistic regression instead of logistic regression). This will increase the statistical power; i.e., we will be able to detect lower odds ratios.

To assess the proxies' ability to predict their family member's preference, we will estimate the overall percentage agreement. Again, the absolute margin of error will be less than 7% (based on a 95% confidence interval). We will also estimate the agreement stratified by the family member's preference. Other measures of agreement (e.g., chance-corrected agreement) may also be calculated.

Furthermore, we will attempt to use (mixed-effects) logistic regression to examine variables associated with 'correct prediction' (and additionally stratified by the elderly's preference [23]). Only responses where the elderly has a preference ('wants ICU admission' or 'does not want ICU admission') will be included [24]. The analysis will only be carried out if enough elderly patients have a preference (we aim to have at least 5, and preferably 10 preferences, for each predictor variable that is included). The following predictors may be included:

Proxy's prediction, elderly's and proxy's certainty in the proxy's prediction of elderly's preference, proxy's preference, proxy's experience with intensive care, communication about end of life decisions, elderly's gender, proxy's gender, interaction between elderly's and proxy's gender, absolute difference in age between the elderly and the proxy, and proxy's assessment of elderly's frailty. (Predictors with high multicollinearity may be excluded.)

In all analyses where multiple responses are included for each participant or pair, we will use statistical methods that take this into account (e.g., mixed-effects logistic regression instead of ordinary logistic regression).

If free-text comments result in rich data, they will be analyzed by Systematic Text Condensation (STC) [25] and published separately.

4. Project organization

4.1. Research group:

Principal investigator:

[name] [name], SSAI and European Diploma of Intensive Care. Senior consultant at the Department of Surgical Services, Intensive Care Unit, Haukeland University Hospital.

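### The one predictor list for correct prediction includes the proxy's prediction, which determines the outcome if separate models are fitted by the elderly person's preference

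*Combined protocol and SAP*

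**What the plan says.** All of this is in section 3.2 (Protocol) unless stated otherwise.

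- **Outcome and models.** Under Analysis, (mixed-effects) logistic regression is to be attempted for correct prediction, and "additionally stratified by the elderly's preference [23". Only responses in which the elderly person wants or does not want ICU admission enter, so there are two strata.
- **Predictors.** A single list follows, introduced by "The following predictors may be included". It opens with "Proxy's prediction, elderly's and proxy's certainty in the proxy's prediction of elderly's preference". The stratified models have no list of their own.
- **Safeguards.** The list closes with "Predictors with high multicollinearity may be excluded". On numbers, the plan says "we aim to have at least 5, and preferably 10 preferences, for each predictor variable that is included".
- **Response options.** Under Survey construction: "Three response options are provided: wishing admission to intensive care, not wishing admission to intensive care, and wishing to not engage in the decision". The proxy answers both for the elderly person and for him- or herself.
- **Status.** Under Choice of method: "This study has an exploratory design".

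**The concern.** The outcome is built from two answers: the proxy's prediction and the elderly person's preference. Once the second is held fixed by stratifying, the first is the outcome in another coding. Entering it as a predictor means regressing the outcome on itself.

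At stake are the stratified models, which serve the third research question in section 3.1, on what affects a family member's ability to predict. The survey names projection, meaning the proxy's own treatment preference, as one such factor. If proxies do project, a proxy who wants ICU is more often right in one stratum and more often wrong in the other. The stratified models would show this directly, and they are the models that the term disables.

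**Working it through.** The plan states no figure for this model, so there is none to reproduce. The check is algebra, followed by illustrations on assumed inputs.

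**1. Separate models per stratum.** Fix the elderly person's preference. Let q = 1 if the proxy's prediction equals it and 0 otherwise, and let y = 1 if the prediction is correct. Then y = q for every response. Take the linear predictor b0 + b1·q + g·x, where x holds the other predictors. Set b0 = −t and b1 = 2t. The linear predictor is then +t + g·x when y = 1 and −t + g·x when y = 0. As t grows, every response's log-likelihood contribution tends to 0, its maximum, whatever g is. So b1 has no finite estimate and g is not identified. A random intercept does not change this, and no sample size or accuracy rate enters the argument.

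**2. Illustration by counts.** Assumed: 200 pairs × 4 vignettes, 50% of the elderly wanting ICU and the rest not, and proxies 68% correct, 20% opposite and 12% not engage. One simulated data set gave these numbers correct:

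| Elderly person's preference | Proxy predicts ICU | Proxy predicts no ICU | Proxy predicts not engage |
|---|---|---|---|
| Wants ICU | 266/266 | 0/71 | 0/56 |
| Does not want ICU | 0/78 | 285/285 | 0/44 |

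Fitted per stratum, the log odds ratio for the prediction kept rising: 13.1, 23.1, 43.1 and 63.1 after 5, 10, 20 and 30 iterations. Its standard error went from about 1.7 to about 470,000.

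**3. Illustration with correlated vignettes.** In 200 simulated data sets with pair-level random effects (SD 1, assumed), all 400 strata were fully separated. In 100 mixed-effects fits that included the term, every log-likelihood was above −0.00003. The prediction coefficient was 33 to 60 (60 was the imposed bound), and the standard error for the proxy's own preference was at least 400.

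**4. The safeguards.**
- The multicollinearity clause compares predictors with each other, whereas this dependence is between a predictor and the outcome. In the simulation, the variance inflation factor of the prediction against the other ten predictors had median 1.19 and maximum 1.45 (nine of the ten were simulated as unrelated).
- The list holds 11 terms: prediction, two certainties, proxy's preference, ICU experience, communication, two genders, their interaction, age difference and frailty. The rule then asks for 11 × 5 = 55 to 11 × 10 = 110 preferences. The simulated strata averaged 326, so the rule was met while separation remained.

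**5. Adjustment instead of separate models.** Code preference e and prediction q as 1 for ICU and 0 for no ICU. A response is correct when e = q. For a + b·e + c·q to separate the outcome, a > 0 and a + b + c > 0 are needed (the correct cells), together with a + b < 0 and a + c < 0 (the incorrect cells). Adding within each pair gives 2a + b + c > 0 and 2a + b + c < 0, a contradiction. With all four cells occupied, these two main effects therefore do not separate the outcome. In one simulated data set, this model with the proxy's own preference added had standard errors of 0.19 to 0.20.

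**6. Pooled model.** From the table, with predictions limited to ICU or no ICU:
- log odds ratio = ln(266/78) − ln(285/71) = 1.23 − 1.39 = −0.16
- standard error = √(1/266 + 1/78 + 1/285 + 1/71) = 0.18

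The term can be estimated here. The not-engage level cannot: it has 0 correct of 56 + 44 = 100, because every elderly respondent in this subset has a preference. Its coefficient has no finite value.

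**The case against.** The strongest reply is that the plan does not commit to the failing model. The regression is to be attempted, it depends on having enough preferences, and the predictors are optional. The entry is legitimate for the pooled model, and nothing says that every listed item enters every model. This stands and keeps the point minor. It does not remove the point, because no rule keeps the item out of the stratified models.

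A second reply is that stratified, which carries a citation, may mean adjustment for the elderly person's preference. Step 5 shows that separation would then not be complete. The alternative cannot be excluded, but separate models are the plainer reading. The same Analysis text speaks of agreement stratified by the family member's preference, where separate estimates are meant.

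A third reply is that nobody would be misled, since the failure is visible at the first fit. That is largely right. What remains is an avoidable choice made after the data are in.

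Three stronger readings are tempting, and the documents do not support them:
- **That the whole proxy-accuracy analysis fails.** It does not. The agreement percentages and the pooled model without the term do not use it.
- **That the plan misreads the pooled coefficient as a difference in accuracy.** It makes no such claim and only looks for associated variables. Labelling that coefficient, or limiting it to ICU and no-ICU predictions, is optional.
- **That projection will certainly show opposite signs in the two strata.** With an assumed projection effect of log 3, the median odds ratios without the term were 6.5 and 0.15, against 0.97 pooled. In a separate run with projection set to 0 they were 0.97 and 1.02, on the same side of 1 in 52 of 100 runs. Both the sizes and the signs follow from the assumption.

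**Conclusion.** The point holds as a minor correction. Using the list as written in separate models per stratum gives models that cannot be estimated, and neither stated safeguard screens for this. The separation follows from the definition of the outcome and needs no assumed rates. It does rest on reading stratified as separate models. Every simulated odds ratio for the proxy's own preference depends on assumed inputs and only illustrates what the stratified models could show. The models of the elderly respondents' own treatment preferences are unaffected.

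**What to change.** Remove the proxy's prediction from the candidate predictors for the models stratified by the elderly person's preference. This can be done before any data are seen. The item may stay in the pooled model, with one sentence noting that a not-engage prediction can never be correct in this subset, so that level has no finite coefficient. If adjustment rather than separate models is meant, the plan should say so. The cost is one phrase in the list and one sentence. No data collection or sample-size figure changes.

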Intensive Care of Elderly: What do They Wish for Themselves?

NCT05149040

Study protocol and Statistical Analysis Plan

06.06.2021 (version 3, IBM approval)

Project Description

1. Project Title

Treatment preferences of very elderly Norwegians in the event of acute life-threatening illness, and family members' ability to predict these treatment preferences: A self-administered survey.

2. Background

Very elderly patients (aged 80 years and older) are a large and steeply increasing patient population in western intensive care units (ICUs), but the overall benefit of intensive care for these patients remains controversial [1, 2]. Will ICU admission improve survival and quality of life, or will it prolong suffering and delay natural death? In case of medical uncertainty, crucial significance is attached to the patient's treatment preferences, but less than 1 in 4 very elderly ICU patients retain decision making capacity [3]. Therefore, information about the patient's likely will is frequently sought through a family conference.

Knowledge regarding the very elderly's life sustaining treatment (LST) preferences is scarce and has recently been rated as number two of top-ten research-topics by a broad panel of experts [4-6]. To our knowledge, so far no survey instrument for this purpose exists.

Research addressing the accuracy of proxy statements by family members has only shown low to moderate correlation [7, 8]. Both internal and external validity of the existing research addressing proxy accuracy is limited.

3. Study design

The overall goal of this project is to improve critically ill very elderly patients' ICU trajectories by bringing forth knowledge about their treatment preferences, their family members' ability to predict their wishes, and by directing attention to confounders of shared decision-making under uncertainty.

3.1. Research questions:

- Which preferences do very elderly people have regarding LST in the event of acute illness warranting ICU admission?
- How accurate can close family members predict the treatment preferences of a temporarily incapacitated very elderly patient with acute life-threatening illness?
- Are there factors that impact on very elderly patients' LST preferences, and on the ability of a close family member to predict these preferences?

3.2. Preregistration:

We plan to preregister the proposed study on www.ClinicalTrials.gov.

3.2. Protocol:

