To estimate the participants’ preferences regarding life-sustaining treatment, we will calculate the proportion of responses in each category (‘wants ICU admission’, ‘does not want ICU admission’, ‘does not want to engage in the decision’), along with 95% confidence intervals. With responses from 200 patients, we can estimate the preference proportions with an absolute margin of error less than 7%, based on 95% confidence intervals, which we deem sufficient. For example, if 50% of the respondents wanted ICU admission, the corresponding 95% confidence interval would be approx. 43%–57%.

To investigate factors associated with the participants’ LST preference, we will use (mixed-effects) logistic regression analysis. The response variables will be a) having a preference (‘wants ICU admission’ or ‘does not want ICU admission’), b) wanting ICU admission (for the subset who have a preference), or c) ‘does not want to engage in the decision’. Alternatively, we will use multinomial regression for the three preference categories. We will fit two types of models, with the following explanatory variables.

Model 1 (experimental variables):

Gender of vignette patient (two levels), survival vs. mortality framing (two levels).

Model 2 (experimental + observed variables):

Variables from model 1, and additionally age (continuous), gender (two levels), religion (three levels), comorbidity (continuous; Charlson Comorbidity Index), frailty score (continuous; Clinical Frailty

Scale), health-related quality of life (continuous; EQ-5D VAS), and experience with intensive care (two levels).

We will only have statistical power to detect large effects. For example, the effect of a binary predictor with a prevalence of 50% (e.g., the survival vs. mortality framing predictor) must correspond to an odds ratio of at least 2.33 (outcome 50% vs. 70%) for the power to be 80% or greater (with 200 participants). For continuous predictors, an odds ratio of 1.5 for the event rate at one standard deviation above the mean compared to the event rate at the mean, will be sufficient.

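### No planned model is specified to show the overall association of age with preference, or of communication and ICU experience with proxy accuracy, without variables that may lie on their path

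*Combined protocol and SAP*

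**What the plan says.** Section 3.1 asks: "Are there factors that impact on very elderly patients' LST preferences", and asks the same about a family member's ability to predict them.

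The Analysis part of section 3.2 (Protocol) commits to two preference models. Model 1 holds only the vignette patient's gender and the framing. Model 2 is "Variables from model 1, and additionally age (continuous), gender (two levels), religion (three levels"), followed by comorbidity, frailty score, EQ-5D VAS and experience with intensive care. No other preference model with observed factors is described.

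For correct prediction, the same section says that a regression will be attempted if enough elderly respondents state a preference. The list opens with "The following predictors may be included". It contains the proxy's prediction, "elderly's and proxy's certainty in the proxy's prediction of elderly's preference", the proxy's own preference, the proxy's ICU experience, "communication about end of life decisions", both genders and their interaction, the age difference, and the proxy's rating of frailty. The only stated grounds for leaving a predictor out are multicollinearity and a minimum number of preferences per predictor.

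The text after the pre-test results says that respondents rate, scenario by scenario, how certain they are about the answer given. The design is described thus: "This study has an exploratory design".

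**The concern.** Earlier conversations and ICU experience come before the questionnaire. The proxy's certainty about a vignette answer comes after it. Certainty therefore cannot confound the relation between communication and accuracy, but it may carry part of it. The same holds for age, which may influence preferences partly through frailty, comorbidity and self-rated health. With these later variables in the model, the coefficient of the background factor describes only the part that does not pass through them.

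No model without the later variables is specified. A weak coefficient for age could mean that age is unrelated to preference, or that its relation runs through health. If the accuracy list is entered together, the same ambiguity applies to communication, which is the most readily modifiable factor on that list. Section 4.4 says the results will feed a clinical decision aid, so the distinction matters for use. The multicollinearity rule does not help: it takes no account of order, and could drop communication while keeping certainty.

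**Working it through.** **The plan's own figures.** Inputs from the Analysis part: 200 participants, one answer each. Two-sided 5% is assumed, in line with the 95% intervals.
- Binary predictor, 50% vs 70%: OR = (0.7/0.3)/(0.5/0.5) = 2.33. Power with 100 per level is 82.8%, which agrees with the plan's 80% or greater.
- Continuous predictor, OR 1.5 per SD, outcome 50%: power = Φ(√(n·P(1−P))·ln OR − 1.96) = Φ(√50 × 0.4055 − 1.96) = Φ(0.907) = 82%. The plan's claim that 1.5 suffices is reproduced.

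**Age in Model 2.** The documents give no mediated share, so two are assumed. Shares are taken on the log-odds scale.

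| Share of age effect through health | Coefficient shown | OR per SD | One-answer power |
|---|---|---|---|
| None | 0.4055 | 1.50 | 82% |
| A quarter | 0.75 × 0.4055 = 0.3041 | 1.36 | Φ(2.150 − 1.96) = 58% |
| A half | 0.5 × 0.4055 = 0.2027 | 1.22 | Φ(1.434 − 1.96) = 30% |

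The power column leaves out any further loss from correlation between age and the health scores.

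**Communication in the accuracy model.** All path strengths are assumptions. 40% of pairs have talked (C). A mediator K = 0.8·C + N(0,1). logit P(correct) = 0.1 + 0.2·C + 0.9·K.
- Without K: accuracy is about 52.1% vs 70.6%, so OR = (0.706/0.294)/(0.521/0.479) = 2.2.
- Certainty equals K (full mediator): adjusted OR = exp(0.2) = 1.22. Simulated power with 200 pairs and one answer each is about 73% without certainty and about 9% with it.
- Certainty is a noisy marker of K, with reliability 0.7, 0.5 or 0.3: adjusted OR is about 1.5, 1.7 or 1.9.
- No direct effect (0 in place of 0.2): the OR falls from 1.85 to 1.00 if certainty equals K, and to about 1.2, 1.4 or 1.6 at the three reliabilities.
- Weak links (0.3 SD, 0.3 log-odds per SD, direct 0.4): OR goes from about 1.6 to 1.5.
- Certainty unrelated to communication or to accuracy: little or no change.

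The coefficient moves towards the null when the direct and mediated parts have the same sign. How far it moves cannot be read from the documents.

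**The proxy's prediction.** Where the elderly person wants ICU admission, a prediction is correct exactly when the proxy predicts ICU admission; the other stratum works likewise. Within the planned strata this predictor therefore determines the outcome.

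**The case against.** A reader might infer that the plan fixes a regression in which certainty cancels the effect of communication, so that the study will report no effect where there is one. The documents do not support that.
- The accuracy model is to be attempted, and its predictors are optional. Joint entry is allowed but not prescribed.
- That communication raises certainty is plausible but not stated, and a cross-sectional survey cannot verify it. The documents support only the time order.
- Certainty may be a mere marker of what the proxy knows. Much of the association then survives adjustment, as the noisy-marker results show.
- The power figures use one answer per pair. The plan has four correlated answers and drops those without a preference, so they do not describe the planned analysis.

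All of this stands.

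It can also be said that the Analysis part speaks of association in an exploratory study, and that age given frailty is a legitimate target, because the decision aid in section 4.4 is to include frailty scoring. Excluding patients who cannot attend unassisted may also narrow the range of frailty and weaken that path. These points justify keeping Model 2. They do not supply the overall association, and the research question is worded in terms of impact.

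**Conclusion.** The point holds as a gap in specification. For age it does not depend on the optional wording: Model 2 is fixed, Model 1 has no observed factor, and nothing in between is planned. For communication and ICU experience it holds if the listed predictors are entered together, which the plan permits.

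It would be too strong to say that these effects are adjusted away. Only the part running through the later variables is removed, and that is the whole effect only if there is no direct part and the mediator is measured without error. The size is unknown: from 2.2 to between 1.2 and about 1.7 for communication under the stronger assumed links with reliability of 0.5 or more, from 1.6 to 1.5 under the weak ones, and from 1.5 to 1.36 or 1.22 per SD for age.

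The randomised framing and vignette-gender effects are unaffected. Model 2 remains suitable for frailty, comorbidity and quality of life, for which age is a proper adjustment variable. This is a cheap and worthwhile improvement, and no planned analysis is invalid because of it. Including the proxy's prediction within strata is a separate defect in the same list and can be settled in the same edit.

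**What to change.** Keep the planned models as stage 2 and add a stage 1 to each.

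- **Preference, stage 1:** Model 1 plus age, gender, religion and ICU experience, without comorbidity, frailty and EQ-5D VAS. **Stage 2:** Model 2 as planned.
- **Accuracy, stage 1:** communication, the proxy's ICU experience, both genders and their interaction, age difference, and the proxy's rating of frailty. Certainty, the proxy's own preference and the proxy's prediction stay out. **Stage 2:** add certainty and the proxy's own preference, described as answer-level factors. Leave the proxy's prediction out of the analyses stratified by the elderly person's preference.

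Report both stages. Read the overall associations of background factors from stage 1 and the conditional associations from stage 2, and say so in the table headings. State that neither stage proves mediation.

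The cost is a few lines in the analysis plan and one more column of estimates per table. Stage 1 also eases the plan's limit of 5, preferably 10, preferences per predictor. Counting each listed item as one predictor, the full list has 11 and needs 55 to 110 preferences, while stage 1 has 7 and needs 35 to 70.
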